5.2 Exploratory objective(s)

If there is a synergistic effect of TRT and chemoimmunotherapy, the frequency of brain metastases may decrease in the experimental arm, or the time until brain metastases occur may be prolonged. Thus, we will compare the frequency and timing of brain metastases. To explore potential benefits or disadvantages of PCI, we will measure cognitive function before and after chemoimmunotherapy and PCI.

[figure not shown]
It is evident that not all ES SCLC patients benefit from durvalumab. Costs of new therapies has become an increasingly important issue. Identifying those who benefit the most from each therapy, will enable us to better individualize therapy for each patient. There are several benefits for both patients and society. Patients will avoid spending time for futile therapy, avoid unnecessary toxicity, and may be offered other, more effective treatments. More targeted therapy will reduce costs, but also better use of our health services' resources. Thus, the biomarker analyses may have significant implications for future clinical practice and research.

6. Study design

6.1 Overview of study design

International, randomized phase III trial. Patients will be randomized 1:1 stratified for established prognostic factors (presence of brain metastases, and presence of liver metastases) to receive chemoimmunotherapy plus TRT or chemoimmunotherapy alone.

Figure 1 Study flow chart

6.2 Study oversight for safety evaluation

A Data and safety monitoring committee (DSMC) will monitor the incidence and nature of all SAEs when 5, 15 and 30 patients have received 3 or more courses of chemoimmunotherapy and TRT and then every 6 months until all patients have completed study treatment to ensure patient safety. The members of the DSMC will be experienced clinicians and a statistician. Following each data review, the DSMC will provide recommendations to the Chief Investigator as to whether the study should continue or be amended, or whether the study should be stopped due to safety concerns (i.e., evidence of harm). The Chief Investigator will, together with the National Coordinating Investigators, make decisions on the basis of the DSMC recommendations. Any outcomes of these safety reviews that affect study conduct will be communicated in a timely manner to the investigators for notification of the IRB/REB/IECs.

7. Patient selection

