4.4 Rationale for conducting this study

- Chemotherapy plus an PD-L1 inhibitor is considered a new standard of care for first-line treatment of ES SCLC but is not yet available/reimbursed in all countries. Durvalumab plus platinum/etoposide is one of these new standard regimens. However, the survival benefit is limited, especially for the first 6 months, and a more effective treatment is needed.
- A more effective initial therapy might improve survival the first 6 months and long-term survival.
- It has been demonstrated that TRT improves survival in ES SCLC, and the effect in terms of PFS is immediate.
- Several studies suggest a synergistic effect of combining RT and ICI. Concurrent administration appears to be the most effective approach, and we will administer the TRT between the second and third chemoimmunotherapy courses. This is deemed to be the earliest time point that TRT may be administered at all sites. We know that SCLC patients may achieve a substantial response to one chemotherapy course (*Halvorsen*, 2016) and believe that administering TRT earlier than in the CREST trial will make it easier to locate the target lesions, increases the likelihood of irradiating viable tumor cells, and consequently increase the chance for achieving a synergistic effect of the TRT and the immunotherapy and not merely an additive effect.
- Combining high-dose TRT, platinum doublet chemotherapy and ICI appears to be well tolerated. Thus, combining medium dose TRT with durvalumab and carboplatin/etoposide should be feasible and well tolerated. However, since there is no data on this combination, investigating whether ading TRT increases the frequency or severity of side effects is an essential part of this trial.
- The benefits and tolerability of PCI in ES SCLC patients receiving chemotherapy plus ICI are unknown.
 We will compare the timing and frequency of brain metastases between patients who receive PCI and those who do not. Furthermore, we will measure and compare cognitive function before and after PCI.
- The survival benefit from adding ICI does not appear before after 6 months. Thus, we restrict the protocol for patients in performance status 0-1. In a previous trial on chemotherapy in ES SCLC, median OS was below 6 months among patients with a PS of 2 or more.

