8.3 Thoracic radiotherapy

8.3.1 Timing

Ideally, patients randomized to the experimental arm are to receive TRT between the second and third chemo-immunotherapy course. TRT may start concurrently with the second course, and TRT should be completed before the third chemo-immunotherapy course commences.

However, there might be logistical challenges if chemo-immunotherapy courses are delayed due to toxicity from chemo-immunotherapy. In case, TRT may start after the second course even if the second course is delayed, but TRT may also start as scheduled regardless of the delay of the second chemo-immunotherapy course (i.e. 21-28 days after the first day of the first chemo-immunotherapy).

If TRT is delayed due to intercurrent disease prohibiting TRT starting as planned, TRT should be administered as soon as possible. If TRT is not administered, patients should still receive chemo-immunotherapy as scheduled.

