14.4 Determination of sample size

[figure not shown]
The sample size calculation assumes an accrual period of 30 months and that the primary survival analysis is performed 14 months after last patient entry. Additional survival analyses will be performed 2, 3, 4 and 5 years after last patient entry. All patients will be followed for a maximum of 5 years when the final survival

analysis will be performed.

Furthermore, the calculation is based on a constant hazard ratio of 0.65, corresponding to median survival times of 13.10 months for the control group and 20.02 months for the experimental group, and 1-year survival rates of 53% in the control group and 66% in the experimental group. This effect was selected as an effect of clinical relevance and an effect of this magnitude might be anticipated if there is a synergistic effect of combining radiotherapy with durvalumab.

The criterion for significance (alpha) has been set at 5%. The test is

2-tailed, which means that an effect in either direction will be interpreted. For this study design, alpha and tails, the population effect size described above, and to have power of 80% to yield a statistically significant result, 128 patients are required in each treatment group.

Enrolment will continue until 128 or more patients in the control arm have completed minimum three chemo-immunotherapy courses, and minimum 128 patients in the experimental group have completed minimum three chemo-immunotherapy courses plus TRT of 30 Gy. We expect a loss to follow-up and inability to complete three courses (plus TRT in the experimental group) of maximum 15% and estimate that we need to enroll a total of 302 patients.

All eligible patients who are randomized will be included in the primary efficacy analyses (ITT-population). All patients who commence chemo-immunotherapy will be included in the toxicity analyses. In addition, we will perform analyses of the patients who complete minimum three chemo-immunotherapy courses (and TRT in the experimental arm) (per protocol population). The sample size calculation was performed using SPSS Sample Power v3.

15. Ethical and regulatory requirements

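### The first three DSMC safety reviews count only patients who received three courses plus TRT, so early toxicity that prevents course three delays them

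*Protocol*

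**What the plan says.** Protocol section 6.2 says that the DSMC "will monitor the incidence and nature of all SAEs" at set points. The first three come "when 5, 15 and 30 patients have received 3 or more courses of chemoimmunotherapy and TRT". Further reviews follow "and then every 6 months until all patients have completed study treatment to ensure patient safety". After each review the committee advises the Chief Investigator on whether to continue, amend or stop.

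Three other places bear on how the count moves:

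- Section 8.3.1 fixes the order of treatment: "TRT should be completed before the third chemo-immunotherapy course commences". The schedule in section 2 puts the start of TRT at weeks 3 to 4 and course three at week 6.
- Section 8.2.5 ends chemotherapy if a course is postponed by more than three weeks.
- Section 14.4 gives the planning figure for non-completion: "We expect a loss to follow-up and inability to complete three courses (plus TRT in the experimental group) of maximum 15" per cent.

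Section 4.4 explains why tolerability is a central question of the trial: "since there is no data on this combination, investigating whether" TRT adds to the side effects is described there as essential.

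**The concern.** A patient adds to the count in section 6.2 only by receiving TRT and then being alive and fit enough for a third course. Three groups add nothing: patients who die early, patients who become too ill for TRT, and patients whose chemotherapy ends before course three because of toxicity. Early reviews are meant to detect such cases. The number of patients who must be treated to reach a given count rises as the share who reach course three falls, so the timetable slows when early harm is greatest.

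Section 6.2 provides nothing else that would bring the first reviews forward: no count of exposed patients, no calendar date and no threshold of serious events. Because the six-monthly cycle begins only after the third count-based review, a delay there also delays routine oversight.

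**Working it through.** **Reproducing the plan's figure.** Section 14.4 states "128 patients are required in each treatment group" and expects at most 15% non-completion. 128 / 0.85 = 150.6, rounded up to 151 per arm, or 302 in total. This matches "estimate that we need to enroll a total of 302 patients". The planning completion rate is therefore 85%.

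**Inputs.**
- k = 5, 15, 30: review triggers (section 6.2).
- c = share of the experimental arm who receive at least three courses and TRT. The value 0.85 comes from section 14.4. The values 0.70 and 0.50 are my assumptions, to show a range.
- r = experimental-arm accrual = 151 / 30 = 5.03 patients per month. This uses the 30-month accrual period in section 14.4 and assumes a uniform rate.
- L = 6 weeks from course one to course three (schedule, section 2), or about 1.4 months. Entry is treated as the date of course one.

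**Formulas.** Experimental-arm patients needed for k counted patients: n = k / c. Approximate time of the review: t = n / r + L.

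| c | Patients needed (k = 5 / 15 / 30) | Of these, not counted | Months from first patient |
|---|---|---|---|
| 1.00 | 5 / 15 / 30 | 0 / 0 / 0 | 2.4 / 4.4 / 7.3 |
| 0.85 (protocol) | 5.9 / 17.6 / 35.3 | 0.9 / 2.6 / 5.3 | 2.5 / 4.9 / 8.4 |
| 0.70 (assumed) | 7.1 / 21.4 / 42.9 | 2.1 / 6.4 / 12.9 | 2.8 / 5.6 / 9.9 |
| 0.50 (assumed) | 10 / 30 / 60 | 5 / 15 / 30 | 3.4 / 7.3 / 13.3 |

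**Reading the table.**
- At the protocol's own 85%, the third review is 8.4 − 7.3 = 1.1 months later than if every patient counted.
- From 85% to 50%, the third review moves by 13.3 − 8.4 = 4.9 months, and 60 − 35.3 = 24.7 more patients are needed before it.
- The first review moves little: 3.4 − 2.5 = 0.9 months between 85% and 50%.
- At any c, about 7 further experimental-arm patients enter during the six-week lag. That is a property of any rule that waits for week 6, and is not part of this concern.

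**The case against.** Much can be said for the present text, and several stronger readings fail.

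- **A reader might infer that the committee does not see events in patients who do not count.** Section 6.2 has it review all serious adverse events. The trigger sets the date of the review and does not limit the data. Even at 50% completion it would have met twice, at about 10 and 30 experimental-arm patients, before the third review.
- **A reader might infer that full TRT is required.** The text speaks of patients who have received TRT and sets no dose condition. Section 14.4 names 30 Gy for the enrolment target, and section 6.2 does not. A patient who stops TRT early but receives course three may well count, as does one whose course three is delayed but given.
- **A reader might infer that low completion is expected, or that it measures toxicity of the combination.** The only documented figure is at most 15% non-completion, which includes loss to follow-up. Progression, logistics and toxicity of the first two courses also lower completion. TRT starts only two to three weeks before course three, and toxicity that appears after course three does not slow the count at all.
- **Other safeguards exist.** Serious events are reported within 24 hours (sections 13.4.2 and 13.13) and reviewed at once by medical staff at the central trial office (section 17). Section 7.4 allows recruitment to stop if new data show unreasonable risk. Sections 4.2.8 and 4.5.2 cite reassuring data on related combinations.

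All of this limits the size and urgency of the point, but the direction of the effect stands. Case-by-case review by the trial's own office is not the committee's review of incidence. The efficacy interim in section 14.3.4 also counts completers and needs at least 85 per arm, so it comes later. Section 6.2 does not say whether the committee may meet outside the schedule, so that can be neither assumed nor excluded.

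**Conclusion.** The point holds as a weakness in the timing of the early safety reviews. It is not a gap in what the committee sees. Deaths, and toxicity that prevents TRT or course three, push the first three reviews and the start of the six-monthly cycle later. At the planned 85% completion the cost is about 1, 3 and 5 extra patients, and about a month at the third review. A delay of about 5 months at the third review requires completion to fall to 50%, which is an assumption, and rests on uniform accrual. The documents do not support a claim that early harm would go unseen, or that the review is designed as a comparison between arms; section 6.2 does not say the latter. The change is worth making because it costs little and the present rule slows in the situation for which early reviews exist.

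**What to change.** Reword the trigger in section 6.2, and any committee charter. The first three reviews would take place when 5, 15 and 30 experimental-arm patients have started TRT and have either:

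- reached the planned date of course three, whether or not it was given; or
- died or stopped study treatment before that date.

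The second limb is needed. Without it, a patient who dies between the start of TRT and the planned date of course three might still not count.

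Add a calendar backstop: a DSMC review at least every 6 months from the first patient randomised. This also covers patients who never start TRT, whom the new count would still omit.

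If all experimental-arm patients start TRT and accrual is uniform, the reviews would fall no later than about 2.4, 4.4 and 7.3 months, whatever share goes on to course three. The cost is a change of wording, reviews that may fall slightly earlier, and possibly one additional meeting if accrual is slow. The endpoint, alpha and sample size are unaffected.

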7.1 Inclusion criteria

For inclusion in the study patients must fulfill all the following criteria:

Capable of giving signed informed consent which includes compliance with the requirements and
restrictions listed in the informed consent form (ICF) and in this protocol. Written informed consent
and any locally required authorization (eg, Health Insurance Portability and Accountability Act in the
US, European Union [EU] Data Privacy Directive in the EU) obtained from the patient/legal
representative prior to performing any protocol-related procedures, including screening evaluations.

- 2. Age \geq 18 years at time of study entry.
- 3. ECOG performance status of 0 or 1.
- 4. Body weight >30 kg.
- 5. Adequate normal organ and marrow function as defined below:
 - Haemoglobin ≥10.0 g/dL.
 - Absolute neutrophil count (ANC) ≥1.5 × 10⁹ /L.
 - Platelet count ≥100 × 10⁹/L.
 - Serum bilirubin ≤1.5 x institutional upper limit of normal (ULN). This does not apply to patients with confirmed Gilbert's syndrome (persistent or recurrent hyperbilirubinemia that is predominantly unconjugated in the absence of hemolysis or hepatic pathology).
 - ALT (SGPT) ≤2.5 x ULN unless liver metastases are present, in which case it must be ≤5 x ULN.
 - Measured creatinine clearance (CL) >40 mL/min or Calculated creatinine CL>40 mL/min by the Cockcroft-Gault formula (Cockcroft and Gault 1976) or by 24-hour urine collection for determination of creatinine clearance:

Males Creatinin-clearance (mL/min) = $\frac{\text{Weight (kg) x (140 - age)}}{72 \text{ constraints (kg)}}$

72 x serum creatinine (mg/dL)

remales Creatinin-clearance (mL/min) = $\frac{\text{Weight (kg)} \times (140 - \text{age})}{\text{Version}} \times 0.85$

72 x serum creatinine (mg/dL)

- 6. Patient is willing and able to comply with the protocol for the duration of the study including undergoing treatment and scheduled visits and examinations including follow-up.
- 7. Life expectancy of at least 3 months.
- 8. At least 1 lesion in the thorax, not previously irradiated, that qualifies as a RECIST 1.1 target lesion (TL) at baseline and is possible to irradiate to 30 Gy in 10 fractions. Tumor assessment by computed tomography (CT) scan or magnetic resonance imaging (MRI) must be performed within 28 days prior to randomization.
- 9. Histologically or cytologically confirmed SCLC. Mixed histology may be acceptable as long as the SCLC component accounts for more than 90%.
- 10. Stage IV disease according to the TNM v8. Patients with stage III disease are eligible if the disease is too widespread to be treated as LS SCLC.
- 11. Pulmonary function: FEV1 >1 L or >30 % of predicted value and DLCO >30 % of predicted value.
- 12. Female patients of childbearing potential (postmenarcheal, not postmenopausal [>12 continuous months of amenorrhea with no identified cause other than menopause], and no surgical sterilization) should use highly effective contraception and take active measures to avoid pregnancy while undergoing systemic study therapy and for at least 5 months after the last dose.
- 13. Patients with brain metastases are eligible provided they are asymptomatic or treated and stable on steroids and/or anticonvulsants prior to start of treatment.

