- 17. Untreated, symptomatic central nervous system (CNS) metastases. Any neurologic symptoms that developed either as a result of the brain metastases or their treatment must have resolved or be stable either, without the use of steroids, or are stable on steroids and/or anticonvulsants prior to the start of treatment.
- 18. History of active primary immunodeficiency.
- 19. Active infection including tuberculosis (clinical evaluation that includes clinical history, physical examination and radiographic findings, and TB testing in line with local practice), hepatitis B (known positive HBV surface antigen (HBsAg) result), hepatitis C. Patients with a past or resolved HBV infection (defined as the presence of hepatitis B core antibody [anti-HBc] and absence of HBsAg) are eligible. Patients positive for hepatitis C (HCV) antibody are eligible only if polymerase chain reaction is negative for HCV RNA.

- 20. Current or prior use of immunosuppressive medication within 14 days before the first dose of durvalumab. The following are exceptions to this criterion:
 - a. Intranasal, inhaled, topical steroids, or local steroid injections (e.g., intra articular injection).
 - b. Systemic corticosteroids at physiologic doses not to exceed 10 mg/day of prednisone or its equivalent.
 - c. Steroids as premedication for hypersensitivity reactions (e.g., CT scan premedication).
- 21. Receipt of live attenuated vaccine within 30 days prior to the first dose of IP. Note: Patients, if enrolled, should not receive live vaccine whilst receiving IP and up to 30 days after the last dose of IP.
- 22. Female patients who are pregnant or breastfeeding or male or female patients of reproductive potential who are not willing to employ effective birth control from screening to 90 days after the last dose of durvalumab monotherapy.
- 23. Known allergy or hypersensitivity to any of the study drugs or any of the study drug excipients.
- 24. Judgment by the investigator that the patient is unsuitable to participate in the study and the patient is unlikely to comply with study procedures, restrictions and requirements.

Investigational products, dose and mode of administration:

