10.1 Restrictions during the study

The following restrictions apply while the patient is receiving study treatment and for the specified times before and after:

Female patient of child-bearing potential:

• Female patients of childbearing potential who are not abstinent and intend to be sexually active with a non-sterilized male partner must use at least 1 highly effective method of contraception (Table 1) from the time of screening throughout the total duration of the drug treatment and the drug washout period (90 days after the last dose of durvalumab monotherapy). Non-sterilized male partners of a female patient of childbearing potential must use male condom plus spermicide throughout this period. Cessation of birth control after this point should be discussed with a responsible physician. Periodic abstinence, the rhythm method, and the withdrawal method are not acceptable methods of birth control. Female patients should also refrain from breastfeeding throughout this period.

Male patients with a female partner of childbearing potential:

- Non-sterilized male patients who are not abstinent and intend to be sexually active with a female
 partner of childbearing potential must use a male condom plus spermicide from the time of screening
 throughout the total duration of the drug treatment and the drug washout period (90 days after the
 last dose of durvalumab monotherapy). Periodic abstinence, the rhythm method, and the withdrawal
 method are not acceptable methods of contraception. Male patients should refrain from sperm
 donation throughout this period.
- Female partners (of childbearing potential) of male patients must also use a highly effective method of contraception throughout this period (Table 1).

N.B Females of childbearing potential are defined as those who are not surgically sterile (i.e. bilateral salpingectomy, bilateral oophorectomy, or complete hysterectomy) or post-menopausal.

Women will be considered post-menopausal if they have been amenorrheic for 12 months without an alternative medical cause. The following age-specific requirements apply:

 Women <50 years of age would be considered post-menopausal if they have been amenorrheic for 12 months or more following cessation of exogenous hormonal treatments and if they have luteinizing

hormone and follicle-stimulating hormone levels in the post-menopausal range for the institution.

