13.15.3 Pregnancy

Maternal exposure

If a patient becomes pregnant during study participation, study treatment should be discontinued immediately.

Pregnancy itself is not regarded as an AE unless there is a suspicion that the IP under study may have interfered with the effectiveness of a contraceptive medication. Congenital abnormalities or birth defects and spontaneous miscarriages should be reported and handled as SAEs. Elective abortions without complications should not be handled as AEs. The outcome of all pregnancies (spontaneous miscarriage, elective termination, ectopic pregnancy, normal birth, or congenital abnormality) should be followed up and documented even if the patient was discontinued from the study.

If any pregnancy occurs during the study, the investigator or other site personnel should inform the sponsor within 1 day, i.e., immediately, but no later than 24 hours of when he or she becomes aware of it.

The sponsor will work with the Investigator to ensure that all relevant information is provided within 1 to 5 calendar days. Sponsor must report to AstraZeneca Patient Safety using the designated Safety e-mailbox within 7 calendar days or sooner when required, for pregnancies with SAEs and within 30 days for all other pregnancies. The same timelines apply when outcome information is available.

Paternal exposure

Male patients should refrain from fathering a child or donating sperm during the study and for 180 days after the last dose of durvalumab + any drug combination therapy or 90 days after the last dose of durvalumab monotherapy, whichever is the longer time period.

Pregnancy of the patient's partner is not considered to be an AE. However, the outcome of all pregnancies (spontaneous miscarriage, elective termination, ectopic pregnancy, normal birth, or congenital abnormality) occurring from the date of the first dose until 180 days after the last dose of durvalumab + any drug combination therapy or 90 days after the last dose of durvalumab monotherapy, whichever is the longer time period should, if possible, be followed up and documented.

Where a report of pregnancy is received, prior to obtaining information about the pregnancy, the investigator must obtain consent from the patient's partner. The local study team should adopt the generic ICF template in line with local procedures and submit it to the relevant IRB/REB/IEC prior to use.

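### Post-treatment contraception periods disagree: 5 months versus 90 days for women, and section 10.1 omits the 180-day post-combination period that 13.15.3 sets for men

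*Protocol*

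**What the plan says.** **Women.** Inclusion criterion 12, in the synopsis and in 7.1, asks women of childbearing potential to use highly effective contraception during systemic study therapy and "for at least 5 months after the last dose". Section 7.1 opens by saying that patients must fulfil all its criteria. The birth-control exclusion, which covers both sexes (synopsis no. 22, 7.2 no. 21), asks for willingness to use birth control "from screening to 90 days after the last dose of durvalumab monotherapy". Section 10.1 says women must use contraception "throughout the total duration of the drug treatment and the drug washout period", and it defines the washout as 90 days after the last durvalumab monotherapy dose. It then adds: "Cessation of birth control after this point should be discussed with a responsible physician".

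**Men.** Section 10.1 applies the same 90-day washout to condom use. It also says "Male patients should refrain from sperm" donation over that period. Section 13.15.3 (paternal exposure) tells men not to father a child or donate sperm until the longer of two limits has passed. One limit is "180 days after the last dose of durvalumab + any drug combination therapy"; the other is 90 days counted from the final monotherapy infusion. It follows partner pregnancies over that same window.

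**Treatment.** Section 8.2.1 gives every patient chemotherapy courses, and section 8.1.1 gives durvalumab on day 1 of each course. All patients therefore start on the combination. Durvalumab alone follows every four weeks.

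**The concern.** Three things do not fit together.

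- Women have two different minimum periods, one in the inclusion criteria and a shorter one in the exclusion criteria and 10.1.
- Men have a two-part rule in 13.15.3, but 10.1 and the exclusion criterion keep only one part. The missing part concerns combination therapy, which every patient is meant to receive.
- The 90-day washout is counted from a monotherapy dose, so it has no starting point for a patient who stops during chemo-immunotherapy. The protocol foresees early stopping: 8.2.6 lists reasons for discontinuation, and 14.4 allows up to 15% for loss to follow-up and failure to complete three courses (plus thoracic radiotherapy in the experimental arm).

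The stake is fetal exposure. Section 10.1 is headed as restrictions and says they apply during study treatment and for the specified times around it, so a site is likely to take its counselling from there. On that text a woman can be released before inclusion criterion 12 is met. A man who stops early can be released while 13.15.3 still asks him to refrain and still follows partner pregnancies. The scheduled pregnancy tests are tied to durvalumab courses (section 2, footnote h), so none falls in the post-treatment period where the texts differ.

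There is also an eligibility question. A woman willing to use contraception for 90 days but not for 5 months passes the exclusion criterion and fails the inclusion criterion.

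**Working it through.** No statistical figure is involved. The check sets the stated periods side by side and does day arithmetic on the planned schedule.

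**Inputs**

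| Item | Value | Source |
|---|---|---|
| Women, after last dose | at least 5 months | Synopsis and 7.1, inclusion 12 |
| Both sexes, after last monotherapy dose | 90 days | Synopsis exclusion 22; 7.2 no. 21; 10.1 |
| Men, after last combination dose | 180 days | 13.15.3 |
| Men, after last monotherapy dose | 90 days; the longer of the two applies | 13.15.3 |
| Combination courses | weeks 0, 3, 6, 9 = days 0, 21, 42, 63 | Section 2 schedule |
| Monotherapy doses | weeks 13, 17, 21, 25 = days 91, 119, 147, 175 | Section 2 schedule; every four weeks |

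**Women whose last dose is monotherapy.** Both periods run from the same dose. Five calendar months are 150 to 153 days, depending on the start date. The gap is 150 − 90 = 60 to 153 − 90 = 63 days.

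**Men who complete four courses on schedule.** The 180-day part of 13.15.3 ends on day 63 + 180 = 243. Section 10.1 ends 90 days after the last monotherapy dose.

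| Last durvalumab dose | 10.1 ends | 13.15.3 ends | 10.1 is earlier by |
|---|---|---|---|
| Week 13 (day 91) | 91 + 90 = day 181 | day 243 | 62 days |
| Week 17 (day 119) | 119 + 90 = day 209 | day 243 | 34 days |
| Week 21 (day 147) | 147 + 90 = day 237 | day 243 | 6 days |
| Week 25 (day 175) | 175 + 90 = day 265 | day 265 | 0 days |

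If the last etoposide day of course four (day 66) counts as the last combination dose, the 180-day part ends on day 246. The gaps are then 65, 37, 9 and 0 days.

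**Patients who never start monotherapy.** For men who stop after course 1, 2, 3 or 4, 13.15.3 ends on day 180, 201, 222 or 243 (0, 21, 42 or 63, plus 180). The washout in 10.1 has no end date, so the text gives no gap to calculate.

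As an assumption only: suppose a site counted 90 days from the last durvalumab dose of any kind. It would stop on day 90, 111, 132 or 153. That is 180 − 90 = 90 days short of 13.15.3 for men, and 60 to 63 days short of inclusion criterion 12 for women.

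**The case against.** The best defence is that nothing here is impossible to obey. All the periods are minimums, and a site that applies the longest one satisfies every section. Section 10.1 does not tell women to stop at 90 days; it sends that decision to a physician. The wording is also uneven in force. Inclusion criterion 12 and 13.15.3 say *should*, 10.1 says *must*, and the exclusion criterion tests willingness at entry. Section 13.15.3 already requires pregnancies to be reported and followed up. The right periods depend on the Investigator's Brochure and drug labels, which are not shown, so it cannot be proved that 10.1 is the faulty text. The number of patients affected is not given.

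Much of this is fair, and it limits the point to unharmonised minimum periods. It does not remove it:

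- No section tells a site to apply the longest period.
- The advice to see a physician is given only for women and sets no further minimum.
- The *should* in inclusion criterion 12 sits under a heading that makes the criteria compulsory.
- On sperm donation, 10.1 and 13.15.3 give different periods for the same conduct.
- Reporting a pregnancy does not prevent the exposure.

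The 90-day shortfall for patients who never start monotherapy rests on an assumed reading and should carry no more weight than that.

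**Conclusion.** The inconsistency stands. Read as written:

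- The stated periods for women whose last dose is monotherapy differ by 60 to 63 days.
- For men who complete four courses on schedule, 10.1 ends 62, 34 or 6 days too early by the standard of 13.15.3 when the last dose is at week 13, 17 or 21. It agrees with 13.15.3 from week 25.
- Patients of either sex who never start monotherapy have no defined washout under 10.1 or the exclusion criterion.

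The figures for men assume doses on the planned days and day 63 as the last combination dose; delays would shift them. This is a participant-safety matter that should be corrected. It does not touch the endpoint, sample size or analysis.

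**What to change.** State one rule per sex, in identical words, in the synopsis, 7.1, 7.2, 10.1 and 13.15.3. Unless the sponsor confirms other periods from the Investigator's Brochure, use the longest already stated:

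- **Women:** at least 5 months after the last dose of any study drug.
- **Men:** 180 days after the last combination dose or 90 days after the last monotherapy dose, whichever ends later. This applies to contraception and to sperm donation.

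Both rules then also work for a patient who never reaches monotherapy.

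In the same amendment, check the list in 8.2.6 of criteria that need not be met on restart or treatment through progression. It includes inclusion criterion 12, which may be a numbering slip; if so, remove it. Contraception stays covered meanwhile, because the birth-control exclusion is not on that list and 10.1 applies during treatment.

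The cost is wording in one amendment. Compared with 10.1, the required period becomes 60 to 63 days longer for women whose last dose is monotherapy. For men who completed four courses on schedule, it becomes 62, 34 or 6 days longer if the last dose is at week 13, 17 or 21.
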